(e.g., during extinction). Nevin developed behavioral momentum theory (BMT) as a result, which accounts for response persistence and resurgence in some situations but not in others.^{31,32} Our preliminary data suggest that RaC better describes resurgence by adding the principle of reinforcement-value decay using a mathematical formula to account for reinforcement history. Reinforcement-value decay quantitatively accounts for dynamically changing reinforcement conditions, including when all reinforcement ceases during the resurgence test. RaC combines these two well-established principles into a mathematical model that appears to account for resurgence in situations in which BMT has failed. Moreover, RaC is a more general model of resurgence that makes predictions about variables not accounted for by BMT (e.g., response effort; reinforcer quality). In addition, it does so more parsimoniously, with fewer free parameters. Our overarching hypothesis is that RaC-informed differential reinforcement treatments, relative to BMT, will be less susceptible to resurgence of problem behavior: (a) during periods when reinforcers are unavailable during the resurgence test; (b) when reinforcer availability diminishes during reinforcement schedule thinning; and (c) when other response or reinforcement parameters change, such as increases in response effort.

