1.2 Research Significance

Resurgence as Choice theory is based on two well-developed concepts: (a) Individuals allocate proportionally more behavior towards responses that proportionally produce more reinforcement, and (b) the value of different experiences with reinforcers decreases over time. The theory is relatively more parsimonious than behavioral momentum theory and provides more general predictions than behavioral momentum theory.³² In essence, the theory is grounded in the notion that relapse of behavior is governed by the same processes that underlie choice behavior (e.g., destructive behavior and appropriate communicative responses).³² The two predictions that are most relevant to our project are (a) resurgence of destructive behavior will decrease with increased DRA treatment duration, and (b) reinforcement schedule thinning show included slow, small decreases in reward deliveries (smaller than those previously reported in the literature). Accordingly, our project will examine the effects of different durations of DRA on resurgence and the effects of adjusting the schedule of reinforcement for each session to include slow and small decreases to avoid resurgence. Findings from this project could have vast clinical implications in that we will demonstrate that time in treatment affects relapse and that schedule thinning can be accomplished without recurrence of destructive behavior.

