1.3 Research Design and Methods

A. Research Procedures

General methods common to Experiments 1 and 2. Potential subjects will receive treatment 3 to 6 hours a day, 5 days a week for about 8-16 weeks depending on the subject's availability. If Experiment 1 is successful at reducing destructive behavior to a desirable level with DRA at a dense schedule, we may conduct Experiment 2 with the same subjects. However, each experiment of the project is independent of the other experiment, and no experiment is required before conducting the other experiment. We may assign subjects to experiments of the project via randomization procedures. Assessment and treatment will be conducted initially in treatment rooms with adjacent observation windows to allow unobtrusive measurement of behavior. Some treatment rooms will have padded walls and floors, which will be used, when necessary, to maintain patient and staff safety. Therapists will conduct multiple sessions daily with each child. We will use controlled, single-case experimental designs (e.g., multielement, reversal) to conduct analyses and

test clinical hypotheses for each child in which subjects serve as his/her own control. We will interpret assessment and treatment results for each child using structured, visual inspection criteria developed and refined by our research team, which have demonstrated reliability, validity, and power to detect differences between test and control conditions with individual children (within-subject; each child serves as his/her own control).^{38,39} A large amount of our methodology will be performed as our standard-of-care procedures in a severe behavior program.

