Our preliminary data⁴⁰ suggest that DRA treatments for destructive behavior like those described below consistently produce at least 85% reduction in baseline rates of destructive behavior after 1-4 DRA sessions. Based on these results, we will set the length of our short-duration condition to approximately 4 sessions. RaC predicts that this short duration of DRA will produce high magnitudes of resurgence during a resurgence test but less resurgence than predicted by BMT. We will compare this short-duration condition with a moderate-duration condition (i.e., approximately 8 sessions of DRA) and an extended-duration condition (i.e., approximately 32 sessions of DRA). RaC predicts that, relative to the short-duration condition, the moderate-duration condition will reduce resurgence only slightly, but the extended-duration condition will reduce resurgence considerably. Each of three durations of DRA (i.e., short, moderate, and extended) will

consist of three phases, a baseline phase, a treatment phase (i.e., DRA), and an extinction phase (i.e., resurgence test). We will conduct this progression of phases three times per participant (i.e., one progression for each duration of DRA), with each progression occurring in a novel stimulus context (i.e., three contexts per participant assigned to conditions randomly), to minimize carryover effects.

Baseline- and DRA-progressive-interval assessment. We will conduct a brief, progressive-interval assessment (PIA) to identify a sufficiently dense schedule of reinforcement for use in subsequent baseline and DRA sessions. The assessment will be identical to the functional-analysis condition with the highest rates of destructive behavior (e.g., the attention condition of the functional analysis for attention-reinforced destructive behavior) with the following exceptions: (a) initially, destructive behavior will be reinforced on a dense schedule of reinforcement, (b) periods of nonreinforcement will begin and increase after every two reinforcer deliveries, and (c) the assessment will end after two reinforcement deliveries corresponding to a nonreinforcement period of 180 s or if untoward effects are observed (i.e., a burst of destructive behavior or negative emotional responding). We will use the results of the PIA to select a dense schedule of reinforcement that does not produce bursts of destructive behavior nor negative vocalizations for use in the baseline and DRA phases.

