Stimulus contexts. Reinforcement effects tend to be specific to the stimulus context in which reinforcement is delivered.⁴¹ Therefore, we will compare the effects of different durations of DRA (i.e., short, moderate, and extended) in equivalent but distinct stimulus contexts. We will correlate each stimulus context with a color, counterbalanced across participants and DRA durations. For example, we will use a blue overhead light, blue alternative communication card, and blue therapist clothing in one progression (e.g., short-DRA duration). We will correlate another progression (e.g., moderate-DRA duration) with yellow, and the final progression (e.g., extended-DRA duration) with red.

Baseline. The baselines will be identical to the functional-analysis condition associated with the highest levels of destructive behavior (e.g., the attention condition for attention-reinforced destructive behavior), except that we will reinforce problem behavior according to a dense, intermittent schedule of reinforcement, using the schedule identified from the PIA. To obtain stable rates of destructive behavior across the baseline conditions, data collection will continue for at least five sessions in each condition once the data in each condition meet the following stability criteria: (a) the standard deviation of the last five sessions is less than 50% of its mean (e.g., $M = 2$, $SD \leq 0.8$) and (b) the baseline trend is flat ($slope \leq |.05|$) or trending upward.

DRA Training. Once the above stability criteria have been met, DRA training will begin in a separate stimulus context (e.g., in a room without an overhead light, with a white alternative communication card and white therapist clothing). In most cases, exchanging a card with a picture of the child consuming the reinforcer (e.g., attention) will be used as the functional (alternative) communication response (FCR) because it can be effectively prompted using gentle physical guidance regardless of the child's functioning level (but other response options, such as card touches or vocal responses, may be used). Reinforcers for the alternative behavior are those functional reinforcers identified in the functional analysis (i.e., the consequence that maintains problem behavior in the natural environment, and the same reinforcer used in baseline). For example, the reinforcer for a child with escape-maintained problem behavior would be a break from academic, pre-academic,

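### Does the option to run Experiment 2 in children who finished Experiment 1 need an analysis rule in the plan?

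*Protocol*

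**What the plan says.** The general methods in Protocol section 1.3 allow overlap between the experiments: "we may conduct Experiment 2 with the same subjects". The condition is that dense-schedule DRA brought destructive behavior down to a desirable level in Experiment 1. The section adds that "each experiment of the project is independent of the other experiment, and no experiment is required before conducting the other experiment", and that "We may assign subjects to experiments of the project via randomization procedures". Independence here means that neither experiment is a prerequisite for the other; it does not promise separate samples.

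Section 4.3 counts the samples additively: 12 recruited and 11 retained for Study 1, 10 recruited and 9 retained for Study 2, 22 and 20 in total. It estimates 45 eligible children a year against a maximum of eight needed.

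Within Experiment 1, section 1.3 guards against carryover by running the three progressions "with each progression occurring in a novel stimulus context (i.e., three contexts per participant assigned to conditions randomly), to minimize carryover effects". For Experiment 2 it specifies a single context and does not say whether that context is new for a child who came through Experiment 1.

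The SAP (Experiment 2) compares the test group with published controls by odds ratios and Fisher's exact test, per case and per schedule step. It does not mention children with Experiment 1 exposure.

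**The concern.** The Experiment 2 outcome is resurgence, and section 1.2 lists as one of its two most relevant predictions that "resurgence of destructive behavior will decrease with increased DRA treatment duration". The objectives in section 1.1 describe RaC as "using a mathematical formula to account for reinforcement history", so history matters by the protocol's own theory. A child who completed Experiment 1 would bring about 4 + 8 + 32 = 44 DRA sessions and three extinction tests into Experiment 2. Section 1.3 expects study procedures to take about 3 weeks of an 8 to 16 week admission, so both experiments could fall within one stay.

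The controls are published cases, so randomization cannot balance prior exposure. A lower resurgence rate in the test group could then partly reflect the earlier DRA and not RaC-informed thinning. Section 1.10 says a favourable Experiment 2 result would lead to a proposal for a randomized trial, so a spurious difference would have consequences.

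**Working it through.** The plan gives no figure for the number of children reused or for the size of any carryover, so there is no stated figure to reproduce. The check has two parts.

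**1. What the sections imply together**

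- *Is reuse planned?* The section 4.3 totals, 12 + 10 = 22 and 11 + 9 = 20, read naturally as different children. With 45 eligible a year and at most eight needed, there is no recruitment reason to reuse anyone. The wording in section 1.3 is an option.
- *Which way would prior exposure push?* Besides 44 DRA sessions and three extinction tests, Experiment 1 includes three baselines of at least five sessions each. That is at least 3 × 5 = 15 sessions in which destructive behavior is reinforced on a dense schedule, which pushes against the DRA effect.
- *Would the effect last?* The duration prediction concerns DRA followed by an extinction test in the same context. Experiment 2 starts with its own baseline, reinforcing destructive behavior continuously or nearly so, and then runs new DRA to stability. Section 1.3 holds that "Reinforcement effects tend to be specific to the stimulus context in which reinforcement is delivered", and section 1.2 that "the value of different experiences with reinforcers decreases over time". Both suggest attenuation. Neither shows that carryover is nil.

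**2. How large the effect on the per-case test could be**

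Inputs from the documents: 9 retained Experiment 2 children (section 4.3), and control prevalence 19/25 = 0.76 (section 1.1). Assumptions: control applications are independent, thinning has no true effect, Fisher's test is two-sided at 0.05, *m* of the 9 children are reused, and their prevalence is 0.76 × (1 + *c*).

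Test-group events = Binomial(*m*, 0.76(1 + *c*)) + Binomial(9 − *m*, 0.76). Control events = Binomial(25, 0.76). The false RaC-favouring rate is the total probability of all outcomes with p ≤ 0.05 and lower prevalence in the test group, by exact enumeration. With *m* = 0 it is 2.0%.

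| Assumed change in prevalence, *c* | *m* = 1 | *m* = 2 | *m* = 3 | *m* = 5 | *m* = 9 |
|---|---|---|---|---|---|
| −10% (0.684) | 2.2% | 2.5% | 2.8% | 3.5% | 5.3% |
| −25% (0.57) | 2.6% | 3.4% | 4.4% | 7.0% | 15.5% |
| −50% (0.38) | 3.2% | 5.2% | 7.9% | 16.9% | 47.4% |
| +10% (0.836) | 1.7% | 1.5% | 1.3% | 1.0% | 0.5% |
| +25% (0.95) | 1.4% | 0.9% | 0.6% | 0.2% | <0.1% |

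The odds ratio produced by carryover alone, with *m* = 2 and *c* = −25%:

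- mean prevalence = (2 × 0.57 + 7 × 0.76)/9 = 6.46/9 = 0.718
- odds ratio = (0.718/0.282)/(0.76/0.24) = 0.80, where the true value is 1

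For *c* = −10%, −50% and +10% it is 0.91, 0.66 and 1.10.

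**Cost of a fixed exclusion.** If two of the nine were reused and dropped from the main comparison, two-sided Fisher power for 0.38 against 0.76 with 25 controls falls from about 0.47 (n = 9) to about 0.42 (n = 7). These values serve only to compare the two sample sizes. The SAP's 0.89, stated for 12 participants, is a separate matter and plays no part here.

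**The case for a change.** The best case for a change is that the option exists, the SAP is silent, and the remedy would be two or three sentences. Deciding after the results are known which children count would leave the case set open to influence. Section 1.3 itself treats carryover as real enough to need a new context for each progression, yet promises none to a child moving into Experiment 2. Reuse also depends on success in Experiment 1, which may select responders and so favour the test group. With nine cases, two reused children can move the odds ratio to 0.80 or 0.66 under the larger assumed reductions.

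Much of this stands as description. Reuse is permitted, and the SAP does not say how such a child would be handled. The responder point is weaker, because thinning in Experiment 2 starts only after an initial demonstration that DRA works, so every test child has passed a similar filter. The confounding claim also needs test and control children to differ in prior DRA, and the documents do not give the controls' history. The larger limitation, non-concurrent published controls, is there with or without reuse.

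Restricting the main analysis to unexposed children would be a trade-off, given the power cost above. Keeping everyone in and showing the result both ways is equally defensible. The choice can be made sensibly at reporting, because section 1.3 has each child's data analysed individually and a reused child would be identifiable.

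**Conclusion.** No change to the plan follows. Followed as budgeted in section 4.3, Experiment 2 has its own children and the question does not arise. If one or two of nine were reused, with a prevalence reduction of 25% or less, the false RaC-favouring rate would be 2.2 to 3.4% against 2.0%. An increase in prevalence would push it below 2.0%. The highest rates, up to 47.4%, need most or all children reused together with strong carryover, and nothing in the documents plans the first or supports the second.

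The result rests on assumed numbers reused and assumed carryover, on 25 independent control applications, and on the per-case test; the per-schedule-step test was not modelled. What remains is an unwritten policy for an optional step. Should a child cross over, an analyst would identify that child and show the Experiment 2 odds ratios with and without the case.

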1.4 Preliminary Data

Our preliminary data⁴⁰ suggest that DRA treatments for problem behavior like those described below consistently produce at least an 85% reduction in baseline rates of problem behavior after 1 to 4 DRA sessions. Based on these results, we will set the length of our short-duration condition to 4 sessions. RaC predicts that this short duration of DRA will produce high magnitudes of resurgence during a resurgence test, but less resurgence than predicted by BMT. We will compare this short-duration condition with a moderate duration condition (i.e., 8 sessions of DRA), and an extended-duration condition (i.e., 32 sessions of DRA). RaC predicts that, relative to the short-duration condition, the moderate-duration condition will reduce resurgence only slightly, but the extended-duration condition will reduce resurgence considerably.

1.5 Sample Size Justification

With a minimum expected reduction in the per-case prevalence of 50% across 12 participants, we estimate a power of 0.89 with alpha=0.05. In addition, on a per-schedule-step basis, the power increases to 0.98 with alpha=0.05. We will assess the adequacy of RaC and BMT in describing the data.

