Limitations of DRA. Although highly effective, DRA has a number of limitations¹⁷⁻²¹ that compromise its effectiveness when implemented by caregivers in the natural environment. In the latter stages of DRA, caregivers are trained to implement treatment, and it is critical that they do so with high procedural integrity (e.g., 90% accuracy), which is more likely if the intervention is practical and compatible with their daily routine. Researchers have identified two important practical limitations of DRA that can interfere with accurate caregiver implementation, namely that treated individuals request reinforcement via the FCR (a) at exceedingly high rates (e.g., request to escape every adult directive) or (b) when it is difficult for the caregiver to deliver reinforcement (e.g., requesting attention when a parent is changing an infant sibling). Our research team and others have used reinforcer-schedule thinning procedures to address these limitations and improve the practicality of DRA.^{21,23} Reinforcer schedule thinning involves progressively and systematically reducing the amount of reinforcers available during treatment sessions. This process is conducted in order to prepare the treatment to be practically used when reinforcers cannot always be feasibly delivered. Unfortunately, in the first large study on reinforcer-schedule thinning, we found that DRA was ineffective in 14 of 25 applications when schedule thinning reached a practical endpoint.²¹ In most cases, it was necessary to add a more restrictive and intrusive punishment component to DRA in order to thin the schedule and also maintain low rates of destructive behavior. A recent replication of this large study reported somewhat more favorable outcomes, but DRA plus schedule thinning still only maintained a 90% reduction from baseline in 11 of 23 applications (48%).²³ In addition, other recent studies have found that when participants treated with DRA were subsequently exposed to extinction of the FCR (or thin reinforcement schedules), treatment relapse often occurred in the form of resurgence of destructive behavior.²⁴⁻²⁶ Similarly, in the first large scale study examining the prevalence of resurgence during schedule thinning, we found that resurgence occurred in 19 out of 25 applications or 76%.²⁷ Collectively, the limitations stated above are evidence for continued refinement to DRA procedures to increase efficacy. In the same way, it is imperative that we develop more durable procedures that will reduce the likelihood of resurgence (i.e., relapse of destructive behavior). These limitations of DRA are actually predicted by a quantitative model derived from behavioral momentum theory. Behavioral momentum theory is a quantitative theory that predicts that DRA, as it is typically implemented, actually promotes resurgence and resistance to extinction for destructive behavior when the FCR is exposed to extinction or thin reinforcement schedules. More importantly, behavioral momentum theory provides clear quantitative guidance on how DRA procedures might be altered in order to mitigate or prevent treatment relapse.²⁸ Several lines of research have used behavioral momentum theory as a guide to develop more efficacious DRA procedures. Unfortunately, recent developments suggest that behavioral momentum theory may not

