We will develop and then assess an alternative schedule-thinning progression for use with children receiving DRA for destructive behavior that we predict to greatly reduce or prevent resurgence of destructive behavior during schedule thinning. One advantage of RaC over BMT is that with RaC we can update our prediction model dynamically after each session during schedule thinning. The prediction of RaC regarding how many reinforcers should be programmed for the next session would change as a result of this recent episode of responding (or lack thereof). We will use this feature of RaC to guide schedule thinning in our test group. The control group will be based on typical responding during reinforcer-schedule thinning observed in the published literature, much of which is based on research from our own clinic (see below). Thus, we do not intend to enroll participants prospectively into the control group. Baseline, DRA training, DRA, and stimulus context. Baseline, DRA training, and DRA procedures will be identical to those conducted in Experiment 1 except that destructive behavior and the alternative response (i.e., the FCR) will be reinforced on a continuous (or near-continuous) schedule in baseline and DRA sessions, respectively. DRA training will be conducted in a manner identical to the procedures used in Experiment 1. The baseline and DRA sessions will continue until the stability criteria specified for Experiment 1 are met. All sessions will be conducted within one stimulus context, as described above.

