DRA schedule thinning. Following an initial demonstration of the efficacy of DRA in which the participant is taught the FCR to access the reinforcer maintaining problem behavior, we will initiate DRA schedule thinning by introducing and then systematically lengthening periods of time in which that reinforcer is unavailable. Periods in which the reinforcer is available and unavailable will be signaled using strategies most relevant to the child's treatment and skill-level, such as different colored stimuli (e.g., green and red wristbands), the presentation and absence of work materials, or the presentation and absence of the communication materials. For schedule-thinning steps, we will use the quantitative models of RaC Theory and the results of a corresponding study with nonhuman animals to dynamically adjust each upcoming schedule-thinning step. We will use additional teaching procedures (e.g., prompting, blocking) as necessary to facilitate schedule thinning, as we would clinically. DRA schedule thinning will continue until the stability criteria specified for Experiment 1 are met under terminal schedules that are similar to those found within our control group. We will then compare these data to a control group consisting of the published data depicted in Briggs et al.²⁷ and reviewed by Saini et al.⁴² We will compare our results from the test group in the current study to the published data to determine whether RaC-informed schedule thinning substantially reduced resurgence compared to traditional schedule-thinning methods published in the literature.

B. Data Points

Dependent variables and measurement. The primary dependent measure will be the rate of destructive behavior (aggression, property destruction, self-injurious behavior) assessed via direct observation. Aggression will be defined as forceful pushing or striking others with body parts (e.g., pushing, hitting, kicking, head-butting), hitting others with objects or throwing objects at others, pinching, scratching, or biting. Property destruction will be defined as forceful banging, throwing, overturning, tearing or climbing on objects not made for that purpose. Self-Injurious Behavior will be defined as forceful striking, scratching, rubbing, poking or biting ones own body parts such that

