1.6 Study Variables

A. Independent Variables, Interventions, or Predictor Variables

Study 1.

Extended DRA. This intervention involves conducting DRA treatment for approximately 32 sessions.

Moderate DRA. This intervention involves conducting DRA treatment for approximately 8 sessions.

Short DRA. This intervention involves conducting DRA treatment for approximately 4 sessions.

Study 2.

RaC-Informed Schedule Thinning. For schedule-thinning steps, we will use the quantitative models of RaC Theory and the results of a corresponding study with nonhuman animals to dynamically adjust each upcoming schedule-thinning step. We will use additional teaching procedures (e.g., prompting, blocking) as necessary to facilitate schedule thinning, as we would clinically.

Traditional Schedule Thinning. We will look to the published literature to identify studies in which schedule-thinning was conducted arbitrarily (i.e., not in accordance with the predictions of RaC).

B. Dependent Variables or Outcome Measures

Study 1.

Rate of destructive behavior during the Resurgence Test following Extended DRA. We will collect continuous, direct-observation measures of destructive behavior throughout all phases of the study.

Rate of destructive behavior during the Resurgence Test following Moderate DRA. We will collect continuous, direct-observation measures of destructive behavior throughout all phases of the study.

Rate of destructive behavior during the Resurgence Test following Short DRA. We will collect continuous, direct-observation measures of destructive behavior throughout all phases of the study.

Study 2.

Rate of destructive behavior during RaC-informed Schedule Thinning. We will collect continuous, direct-observation measures of destructive behavior throughout all phases of the study.

Rate of destructive behavior during Traditional Schedule Thinning. We will collect continuous, direct-observation measures of destructive behavior throughout all phases of the study.

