4.3 Number of Subjects

A. Total Number of Subjects

We conservatively estimate at least 60% of patients receiving clinical treatment in our program will meet the inclusion criteria. During the project, we will recruit 22 (12 for study 1 and 10 for Study 2) and retain 20 children with severe destructive behavior. We expect 10% attrition.

B. Total Number of Subjects If Multicenter Study

Not Applicable

C. Feasibility

We will recruit 22 and retain 20 children with severe destructive behavior from the Severe Behavior Program. We will recruit 12 and retain 11 children for Study 1, and we will recruit 10 and retain 9 children for Study 2. We conservatively estimate at least 60% of patients will meet the criteria (n = 45 per year available; eight per year needed, maximum). The research team will communicate the recruitment plan to all case managers in the Severe Behavior Program so that case managers can recommend relevant participants. The principal investigator and research staff will meet to discuss recruitment status and resolve any issues related to recruitment.

Additionally, the DDDC has 10 classes with a class size between 5 and 8 patients. Thus, the DDDC has between 50 and 80 patients at a given time. The majority of patients have a diagnosis of ASD, and a large minority of patients are reported to display destructive behavior. We expect that roughly 5-10 patients will be appropriate for the study, and recruitment is deemed feasible.

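### The Experiment 2 power of 0.89 is stated for 12 participants, but section 4.3 plans 10 recruited and 9 retained for Study 2; 12 is Study 1's number

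*Protocol*

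**What the plan says.** Protocol section 1.5, the only sample-size justification, reads: "With a minimum expected reduction in the per-case prevalence of 50% across 12 participants, we estimate a power of 0.89 with alpha=0.05". It then gives 0.98 for the analysis by schedule step. It does not name the study. The SAP prints the same sentence under Experiment 2, after the odds ratios and Fisher's exact test. Per-case prevalence and schedule steps have meaning only in the schedule-thinning study.

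Protocol section 4.3, part A: "we will recruit 22 (12 for study 1 and 10 for Study 2) and retain 20 children with severe destructive behavior". Part C: "we will recruit 10 and retain 9 children for Study 2". Part C also plans 12 recruited and 11 retained for Study 1.

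Section 1.3 adds that, if Experiment 1 succeeds, "we may conduct Experiment 2 with the same subjects".

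On controls, section 1.3 says "we do not intend to enroll participants prospectively into the control group", and later: "We will then compare these data to a control group consisting of the published data depicted in" one cited study and reviewed in a second cited paper. Section 1.6 is looser: "We will look to the published literature to identify studies in which schedule-thinning was conducted arbitrarily". None of these passages gives a number of controls. The only resurgence prevalence in the documents is in section 1.1: "resurgence occurred in 19 out of 25 applications or 76" per cent. It carries the same citation number as the first control source.

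**The concern.** A power figure holds only for its own sample size. Here the size attached to 0.89 belongs to the other experiment, and both sizes planned for Study 2 are smaller. A non-significant per-case comparison could then be read against a power that the planned sample was never shown to have.

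A separate gap makes this harder to repair. The inputs behind 0.89 are missing: number of controls, control prevalence, one- or two-sided testing, and whether 50% is a relative reduction or a drop in percentage points. The per-step 0.98 has no sample size of its own, no number of steps and no statement on dependence between steps within a child, so it cannot be checked.

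**Working it through.** **The sample sizes (no assumption about the power method)**

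| Source | Study 1 | Study 2 | Total |
|---|---|---|---|
| Protocol 1.5 and SAP Experiment 2, n for power | – | 12 | – |
| Protocol 4.3, recruited | 12 | 10 | 12 + 10 = 22 |
| Protocol 4.3, retained | 11 | 9 | 11 + 9 = 20 |

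Section 4.3 expects 10% attrition: 10 × 0.9 = 9. So 12 is not Study 2's figure before or after dropout. The totals are plain sums, with no allowance for a child in both studies.

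**Trying to reproduce 0.89**

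Power of Fisher's test = Σ over a, b of Bin(a; n, p₁) × Bin(b; m, p₀) × 1[Fisher p ≤ 0.05]. Here n is the number of test children, m the number of controls, p₁ the test prevalence and p₀ the control prevalence.

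Inputs:
- α = 0.05 and Fisher's test, from the SAP.
- p₀ = 0.76, from 19/25 in Protocol 1.1; using it as the control rate is an assumption.
- p₁ = 0.76 × 0.5 = 0.38 if 50% is relative, or 0.76 − 0.50 = 0.26 if it is percentage points.
- m and sidedness are not stated.

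With m = 25 (assumed):

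| Reading | Sides | n = 9 | n = 10 | n = 12 |
|---|---|---|---|---|
| 76% to 38% | two | 0.474 | 0.465 | 0.569 |
| 76% to 38% | one | 0.486 | 0.532 | 0.616 |
| 76% to 26% | two | 0.716 | 0.711 | 0.818 |
| 76% to 26% | one | 0.737 | 0.790 | 0.849 |

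No row reaches 0.89 at n = 12. That shortfall comes from the unstated inputs, not from 12 against 10 or 9. Under the relative reading, no control size from 12 to 300 reaches 0.89 at n = 12; the maximum is 0.797. (Power is not always monotone in n because Fisher's test is discrete.)

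**Isolating the effect of the mismatch**

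Take every m from 12 to 200, both readings and both sidedness choices at p₀ = 0.76. Keep the sets whose power at n = 12 rounds to 0.89, then lower n with all else fixed. Eight sets qualify, all with the 50-point drop:

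| Controls | Sides | n = 12 | n = 10 | n = 9 |
|---|---|---|---|---|
| 43 | two | 0.890 | 0.806 | 0.804 |
| 46 | two | 0.892 | 0.817 | 0.779 |
| 47 | two | 0.888 | 0.807 | 0.810 |
| 48 | two | 0.890 | 0.829 | 0.801 |
| 50 | two | 0.890 | 0.817 | 0.781 |
| 51 | two | 0.895 | 0.818 | 0.813 |
| 33 | one | 0.885 | 0.838 | 0.790 |
| 37 | one | 0.886 | 0.837 | 0.812 |

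The loss is 5 to 8 points at n = 10 and 7 to 11 points at n = 9. For example, with 46 controls two-sided, 0.892 − 0.779 = 0.113.

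Sensitivity: accepting 0.88 to 0.90 at n = 12 gives 20 sets (28 to 54 controls) and a loss of 4 to 13 points. Varying control prevalence over 60% to 90% with up to 120 controls gives 85 sets: power 0.73 to 0.85 at n = 9, 0.79 to 0.88 at n = 10, and a loss of 2 to 16 points.

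**The case against.** The best defence is carry-over. Section 4.3 counts recruits, and a child who continues from Experiment 1 is not recruited again, so 22 recruits is compatible with 12 or more children in Experiment 2. This stands as a possible explanation. But section 1.3 makes it optional and conditional on Experiment 1's success, section 4.3 does not use it, and neither document says it was how 12 was reached. It is something the sponsor may state, not something the plan states.

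Second, the loss of power is not proven. The calculation assumes that 0.89 really was obtained at n = 12 with Fisher's test. If 12 is only a slip, 0.89 might belong to another n: at 76% control prevalence with a 50-point drop, one-sided, 17 control sizes between 62 and 91 give 0.89 at n = 10. This also stands. It makes the size of the loss uncertain and leaves the contradiction untouched.

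Third, the practical weight is limited. The Study 2 primary endpoint (stable responding under a terminal schedule) and the single-case analyses do not depend on this figure, and a positive Study 2 would lead to a proposal for a randomized trial. True, but a stated power and its n should still match the study they describe, and correcting them needs no change to the design.

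**Conclusion.** The concern holds. Both documents state the Experiment 2 per-case power for 12 participants, while the protocol plans 10 recruited and 9 retained for that study. This rests on the text alone.

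The numerical consequence is conditional. If 0.89 is a Fisher power at n = 12 with 76% control prevalence, the planned sample has about 0.78 to 0.84, a loss of 5 to 11 points; over the wider assumed range of control prevalence the loss is 2 to 16 points. The correct value cannot be fixed from the documents. The figures with 25 controls should not be read as an effect of the mismatch. They and the halving result show that 0.89 cannot be interpreted until its inputs are given.

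**What to change.** 1. Reconcile 12 with 10 and 9 in Protocol sections 1.5 and 4.3 and in the SAP. If children continuing from Experiment 1 are meant to make up the difference (two to reach 12 from 10 recruited, three from 9 retained), say so and count them in section 4.3.
2. Replace 0.89 with the Fisher power at Study 2's own n. State the number of controls and their source, the control prevalence, one- or two-sided testing, and whether 50% is relative or in percentage points.
3. Recompute 0.98 on the same n, giving the number of schedule steps assumed and whether steps within a child were treated as independent.

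Cost: wording in two protocol sections and the SAP, plus a short recalculation. The stated power is likely to become less favourable, depending on the inputs. No extra patients are needed.
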